5.4 Treatment Delivery

The population that is eligible for this study would not be eligible for RSBY under the program's usual rules. To make this study possible, we exchanged letters of cooperation with the state in which we conducted the study (Karnataka), the central government agency (Ministry of Labor) responsible for administration of RSBY, and the development organization (GIZ) providing technical support for RSBY.

Sample households were randomized in August 2014 using data from the listing exercise. They were informed of their treatment assignment and, depending on which arm to which they are assigned, given access to insurance or cash in May and June 2015. This step took place roughly 18 months after the baseline due to government constraints. Due to challenges associated with evaluating a government program, we were only able to enroll sample households when the government held its RSBY enrollment drive in early 2015.

We enrolled study households much in the same way the government enrolled RSBY (non-study) eligible households into the program: via a mobile enrollment truck that visited each village. One difference is that we went to each household to ask them if they would like to enroll and took them to the enrollment truck, which was parked in one place in the village. By contrast, the government informed non-study households by delivering paper notices (chits) to each home about when and where the enrollment truck would be in the village.

Roughly 78.4%, 70.4% and 58.6% of households in arms A, B, and C, respectively enrolled in RSBY. Enrollment rates are somewhat higher in Gulbarga than Mysore: 77.9/76.4/64.1% v. 78.8/63.5/52.3% in A/B/C. No one in arm D enrolled.

For all study households that take up insurance, we paid the government their premiums. For households in arms A, this was funded by grant funds. For those in B and C that purchase insurance, this was funded by the respondents' money.

The Karnataka government renewed RSBY automatically for non-study and study households in 2016 and 2017 without any action—even payment—by enrollees. RSBY ended in the state on August 31, 2018, to make way for the new NHPS scheme, which is scheduled to start in late 2018 or early 2019. As of this writing, Karnataka had agreed to roll out NHPS but had not begun the roll-out.

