10.3 Price signaling

We test this explanation by testing its prediction that, assuming individuals learn about prices not just from their own experience but also from the experience of their peers, individuals who live in villages where there are more people who received insurance at a lower price (e.g., zero) should perceive insurance as having less value and thus purchase it less themselves. We test this prediction by examining the following:

- Holding constant the group assignment of a household, the household should attempt to or utilize care more the higher is price paid by other households that are both in the study sample and in the same village.

¹⁸The price of RSBY is fixed under our study—and for BPL families in the actual scheme—regardless of the size of the household.

¹⁹By contrast, average utilization could be lower in A than C if you only look at enrollees, i.e., the CATE estimates for A could be lower than for C even if there is selection.

- Holding constant the group assignment of a household, the household should attempt to or utilize care more the higher the price paid by other households that are in the same village, including both other households in the village and the fraction of households in the village that are below the poverty line.

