10.4 Sunk costs

We do not pre-specify any specific assumptions or predictions we are able to test under this explanation. Therefore, we attribute any failure to support the above two explanation as evidence in favor of this third explanation.

11 Are there spillovers from formal insurance?

RSBY may have spillovers that run from program participants to other RSBY participants and to non-participants. As for the former, it has been shown that per-capita program utilization increases with the number of people who utilize the scheme. For example, people hear that the program works by word of mouth so they are more likely to utilize it (Sood et al., 2014). (This is not unique to health insurance schemes.) More sophisticated analyses of technology or program adoption via social networks suggests the same (Banerjee et al., 2013).

As for non-participants, there are at least two ways they may be impacted. First, formal health insurance may impact alternative methods of financing health care expenditures and of financing generally. For example, formal health insurance may substitute for informal health insurance, or it may complement it if formal insurance covers village-level shocks while informal insurance covers household-level shocks. Moreover, formal insurance may impact credit markets by reducing precautionary savings, and thus the supply of credit in village-level credit markets, or reduce the demand for borrowing, and thus the demand for credit in those markets. Moreover, formal insurance may impact asset markets if formally insured people change their asset allocations, and frictions in those markets mean that prices for assets are set at the village level. Second, provision of insurance may lead to congestion at covered providers, to the extent that capacity constraints are present. This would impact both participants and non-participants.

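### Section 10.3 tests price signaling on the price peers actually paid and on the village BPL fraction; neither exposure is randomised and both can move with how many peers are insured

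*Combined protocol and SAP*

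**What the plan says.** Section 10.3 reasons that people learn about prices from their peers, so that cheap insurance nearby lowers its perceived value. The first test is that, within a household's own arm, "the household should attempt to or utilize care more the higher is price paid by other households"; the peers meant here are other study households of that village. The second test widens the peer group to the whole village, including "the fraction of households in the village that are below the poverty line". The section gives no equation and no definition of price paid (per peer household or per enrolled peer). It has no term for the share of peers insured, and it refers neither to Table 1 nor to equation (2).

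Section 5.4 shows who can pay: "Roughly 78.4%, 70.4% and 58.6% of households in arms A, B, and C, respectively enrolled in RSBY", and "No one in arm D enrolled". Arm A was free; B and C households paid only if they bought.

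Two other statements bear on the test. Section 11 says that "per-capita program utilization increases with the number of people who utilize the scheme". Section 10.4 specifies no test for sunk costs and says: "we attribute any failure to support the above two explanation as evidence in favor of this third explanation".

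**The concern.** The wording names an outcome of take-up as the exposure. A village where many B and C households bought differs from one where few did, possibly in health need or trust in the scheme, and those traits can also drive use. That is self-selection at village level.

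A separate problem would remain even if price were randomised. The mix of arms that sets peer price also sets how many peers are insured, and the plan itself treats peer coverage as a cause of use. A slope on peer price then combines two effects.

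The BPL fraction is weaker still. BPL enrollees pay only the INR 30 card charge (Section 4.2), so a higher BPL share lowers peer price and may raise the number of insured neighbours. Section 11.2 lists the same fraction among variables tied to social networks, hospital capacity and local credit, none of which is a price signal.

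At stake is the plan's second evaluation question, on whether and how price affects use. Because of the rule in Section 10.4, an uninterpretable signaling test feeds directly into a conclusion about sunk costs.

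**Working it through.** **Inputs.** Village-arm weights and household shares from Table 1; take-up of 78.4%, 70.4%, 58.6% and 0% in A to D (Section 5.4); premium of about INR 200 (Section 4.2).

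**Reproducing the plan's figure.** The village-weighted A share is 0.15×30 + 0.15×30 + 0.15×30 + 0.35×70 + 0.20×10 = 40%. B, C and D each give 20%. This matches the Total row of Table 1.

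**Formulas, per village arm.**
- Insured share = 0.784A + 0.704B + 0.586C
- Price per peer household = 200 × (0.704B + 0.586C)
- Price per enrolled peer = price per peer household ÷ insured share

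For arm IV: insured = 0.784×0.70 + 0.704×0.10 + 0.586×0.10 = 67.8%; price per household = 200 × 0.129 = INR 25.8; price per enrollee = 25.8 ÷ 0.678 = INR 38.

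| Village arm | Access (A+B+C) | Insured | INR per peer household | INR per enrolled peer |
|---|---|---|---|---|
| I | 90% | 64.6% | 82 | 127 |
| II | 90% | 59.9% | 73 | 121 |
| III | 50% | 36.4% | 26 | 71 |
| IV | 90% | 67.8% | 26 | 38 |
| V | 70% | 46.5% | 77 | 166 |

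**Mixing.** Arms III and IV have equal price per household but differ by 31.4 points in peers insured. Reading price paid as assigned price does not remove this: both arms then average 200 × 0.20 = INR 40 per household, at 50% and 90% access.

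**Correlation of peer price with insured share across the five arms.**

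| Definition | Weighted by village allocation | Unweighted |
|---|---|---|
| Per enrolled peer | -0.41 | -0.17 |
| Per peer household | -0.09 | +0.22 |

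The weighted slopes are 9.7 and 4.2 points less enrolment per INR 100. Even the sign of the correlation depends on choices that Section 10.3 leaves open.

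**Direction of bias.** This was checked by simulation with no price signal present. The effect sizes are assumptions, not document figures: 424 villages of 26 households, base use 15%, two-sided 5% level, 400 runs, and a village demand factor that shifts B and C enrolment by 0.5 logit per SD.
- If demand also raises use by 2 to 3 points per SD, price per household shows a false slope of +2.3 to +3.1 points per INR 100 and rejects in 14 to 22% of runs. Price per enrollee shows +0.7 and rejects in about 7%. Arm IV v I and II pooled rejects in 4 to 5%.
- If instead use rises by 2 points for every 10 points of peers insured, price per enrollee shows -1.3 points per INR 100 (17% rejections), while price per household shows +2.3 (14%).

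**What the assigned contrast leaves.** Arms I, II and IV all have 90% access. Expected enrolment in IV exceeds II by 67.8 - 59.9 = 7.9 points and I by 67.8 - 64.6 = 3.2 points. With district take-up, the gaps v II and v I are 5.5 and 0.6 points in Gulbarga and 10.6 and 6.1 in Mysore. Under the same assumed coverage effect, I and II pooled minus IV shows -1.2 points of use (16% rejections), II minus IV -1.6 (16.5%), and I minus IV -0.7 (6%).

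**The case against.** The strongest reply is that the plan already holds the remedy. Equation (2) regresses outcomes on the randomised shares with own assignment in the model. Equation (3) instruments village enrolment. Section 11.1 names the village-level group as its source of variation. Section 10.3 writes no regression, so it does not commit to an uninstrumented slope on realised price. This stands in part: the tools exist and the change is small. But Section 10.3 invokes none of them, and what it does name is price paid and the BPL fraction.

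Two stronger readings are tempting, and the documents support neither.

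- **That the test is biased toward finding no signal, so the sunk-cost answer is wrong by construction.** The -0.41 correlation invites this, but it is one of several definitions. Self-selection is also not its source: assigned price per household offered insurance correlates -0.42 with enrolment. With take-up set to 70% in all three arms, the per-enrollee figure is still -0.20, because the D share varies across village arms. Village demand pushes the slope the other way. The net direction is unknown.
- **That arm IV v I and II is a clean contrast.** It removes self-selection and unequal access. It does not equalise coverage: a pooled gap of 5.6 points over INR 86 is 6.5 points per INR 100, about two-thirds of the 9.7 across all arms. Arm I is also 50% group B, whose households received cash equal to the premium, so peer cash is mixed with peer price.

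**Conclusion.** The concern holds as a problem of exposure definition. As written, Section 10.3 uses a quantity realised after peers' take-up and a fraction that was never randomised, and both can move with peer coverage. A positive, null or negative result could not be read as evidence for or against price signaling, and Section 10.4 should not turn a null into support for sunk costs.

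The arm-level prices and insured shares rest on document figures, taking the premium as INR 200 and arm-average take-up as the same in every village arm. The size and direction of bias rest on assumed effects and are not established. Assignment-based exposure is an improvement, not a complete separation of price from coverage. This is worth changing before the endline analysis; it does not affect the main ITT estimates.

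**What to change.** 1. Define the exposure in Section 10.3 by assignment. In equation (2), within household arm, test the A share against the B and C shares with the D share held fixed.
2. Alongside it, report village arm IV v II and IV v I separately, not pooled.
3. Do not use realised price or the BPL fraction as the causal exposure. If they are kept, label those analyses descriptive and define price paid.
4. State the limits: expected peer enrolment differs by about 8 points (IV v II) and 3 points (IV v I), and arm I carries group B's cash grant. Use III v IV to gauge the coverage effect at equal price per peer household, noting that price per enrolled peer still differs there (INR 71 v 38).
5. Amend Section 10.4 so that a null signaling result alone is not evidence for sunk costs.

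The cost is a change of wording, with no new data. The direct arm contrasts draw on 15 + 15 + 35 = 65% of villages (about 276 of 424), so they are less precise; the share model uses all villages but relies on its parametric form.

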10.4 Sunk costs

We do not pre-specify any specific assumptions or predictions we are able to test under this explanation. Therefore, we attribute any failure to support the above two explanation as evidence in favor of this third explanation.

11 Are there spillovers from formal insurance?

RSBY may have spillovers that run from program participants to other RSBY participants and to non-participants. As for the former, it has been shown that per-capita program utilization increases with the number of people who utilize the scheme. For example, people hear that the program works by word of mouth so they are more likely to utilize it (Sood et al., 2014). (This is not unique to health insurance schemes.) More sophisticated analyses of technology or program adoption via social networks suggests the same (Banerjee et al., 2013).

As for non-participants, there are at least two ways they may be impacted. First, formal health insurance may impact alternative methods of financing health care expenditures and of financing generally. For example, formal health insurance may substitute for informal health insurance, or it may complement it if formal insurance covers village-level shocks while informal insurance covers household-level shocks. Moreover, formal insurance may impact credit markets by reducing precautionary savings, and thus the supply of credit in village-level credit markets, or reduce the demand for borrowing, and thus the demand for credit in those markets. Moreover, formal insurance may impact asset markets if formally insured people change their asset allocations, and frictions in those markets mean that prices for assets are set at the village level. Second, provision of insurance may lead to congestion at covered providers, to the extent that capacity constraints are present. This would impact both participants and non-participants.

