8.5 General coloring variables

The following is a non-exhaustive list of variables that may be used as control variables that measure dosage, specific margins of response or dosage. This list is non-exhaustive as it lists only those variables measured at endline and not otherwise included as a coloring variable above.

- Gender of respondent
- Age of respondent
- Role of respondent in household (relationship to head of household)
- Size of household
- Number of adults in household
- Number of children in household
- Knowledge of BPL households and how many
- Knowledge of BPL households with RSBY cards and how many
- Knowledge of household that successfully used RSBY
- Knowledge about RSBY (number correct out of 4 questions)
- Knowledge of when RSBY scheme expired
- Subjective willingness-to-pay for RSBY
- Knowledge about NHPS
- Does respondent think household is covered by NHPS
- One item test of NHPS (does respondent know about amount of coverage)
- Did any other individuals assist with answering questions during the survey? If so, what is the gender and relationship to respondent? ¹⁷

¹⁷Additional respondents may affect the response quality in both positive and negative ways. For finance questions, these individuals may improve the precision of the responses. For health questions, these individuals may lead to decreased precision. Please note that enumerators were instructed to administer health questions without any additional individuals present to minimize this concern.

9 Structural modeling

We plan to develop an economic model of household financial decisions and health status. We will structurally estimate the model using the experimental variation, to quantitatively reconcile the rich set of empirical results and perform counterfactual analysis.

10 Why is higher price for insurance associated with higher utilization?

At midline we found that individuals in group C, which had to pay a premium for insurance but did not get an unconditional cash transfer, had higher rates of utilization of the RSBY card. We will explore three explanations. First, individuals that value insurance more because they are more likely to use it are more likely to take up insurance, i.e., there is selection. Second, a higher price for a good sends a positive signal about the quality of the good, and higher quality goods are consumed more. Third, there is some sunk cost effect.

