We will test this finding again at endline, and we will test which of these explanations for the midline finding (and potential endline finding) have merit. Our specific analyses are listed below.

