10.1 Higher price causes greater utilization

We test whether the midline finding persists at endline in two ways:

- We examine whether group C households have higher rates of attempts to use RSBY and successful efforts to use RSBY.
- Because households with more members have a lower effective price per member¹⁸, larger households should have greater utilization per capita (as opposed to per household).

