10.2 Selection

We test this explanation by testing its assumptions or predictions:

- Individuals who were differentially sick or risk averse at baseline are more likely to enroll in RSBY in the first place and/or retain the RSBY card at midline and endline, conditional on household group assignment.
- Total utilization should be weakly higher in household group A than C. Equivalently, average utilization including both enrollees and non-enrollees, i.e., the ITT estimates of utilization, should be higher in A.¹⁹
- After predicting those in group A likely to enroll if they were in group C, we test to see if they have higher utilization conditional on getting insurance.

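### Section 10 credits an untested sunk-cost explanation by default (10.4), and its household-size check (10.1) predicts the opposite of the finding it is meant to confirm

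*Combined protocol and SAP*

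**What the plan says.** The opening of Section 10 reports that group C had higher card use at midline. It names selection, price signalling and sunk costs as candidate causes ("We will explore three explanations") and promises that "we will test which of these explanations for the midline finding (and potential endline finding) have merit".

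- **Section 10.2 (selection)** lists three checks. One is that "Total utilization should be weakly higher in household group A than C"; its footnote 19 separates this all-assigned comparison from one among enrollees only.
- **Section 10.3 (price signalling)** lists two checks.
- **Section 10.4 (sunk costs)** lists none: "We do not pre-specify any specific assumptions or predictions we are able to test under this explanation". It then draws the consequence that "we attribute any failure to support the above two explanation as evidence in favor of this third explanation".
- **Section 10.1**, whose heading asserts that a higher price leads to more use, begins "We test whether the midline finding persists at endline in two ways". The first way compares group C's attempted and successful card use. The second reasons that "households with more members have a lower effective price per member", so "larger households should have greater utilization per capita (as opposed to per household"). Footnote 18 adds that the price does not vary with household size.

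**The concern.** **Section 10.4.** An explanation with no prediction of its own cannot be shown to have merit, yet this one gains whenever the others are not supported. The rule leaves three things open: whether one or both rivals must fail, how three selection checks and two signalling checks combine into a failure, and whether there is still anything to explain at endline. The plan itself speaks only of a potential endline finding. The three explanations are not said to be exhaustive or mutually exclusive.

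**Section 10.1.** The household-size bullet is offered as a check that higher price goes with higher use. Its argument runs from lower price to higher use, which is ordinary downward-sloping demand. A result pointing against the midline finding would be recorded as the finding persisting.

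At stake is the second half of evaluation question 2 in Section 3, how insurance prices affect utilization, together with the reading of one persistence check.

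**Working it through.** The plan states no figure for Section 10, so there is nothing to reproduce. The power statement in Section 5.1 (a 25% change in hospitalization, 10% attrition) gives no alpha, power level or base rate, and cannot be carried over to these checks.

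**1. How often the Section 10.4 trigger fires (illustration).** Assumptions, none from the plan: one independent test per explanation, alpha 0.05, selection true with power p, signalling false.

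- Both must fail: (1 - p) x 0.95. At p = 0.8 this is 0.2 x 0.95 = 19%; at p = 0.5 it is 0.5 x 0.95 = 47.5%.
- Either may fail: 1 - p x 0.05. At p = 0.8 this is 96%; at p = 0.5 it is 97.5%.
- None of the three true: 0.95 x 0.95 = 90.25% (both), or 1 - 0.05 x 0.05 = 99.75% (either).

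Under the same assumptions, if sunk costs were the only true cause, selection and signalling would both be false. The trigger would again fire 90.25% or 99.75% of the time. It therefore fires as often when sunk costs is right as when nothing on the list is right, and cannot tell these two cases apart.

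**2. What the A-versus-C selection check can show.** Enrolment rates are from Section 5.4. With no card use among non-enrollees, ITT card use is the enrolment rate times use per enrollee. At equal use per enrollee, the A/C ratio is:

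| | A (%) | C (%) | A/C |
|---|---|---|---|
| Overall | 78.4 | 58.6 | 1.34 |
| Gulbarga | 77.9 | 64.1 | 1.22 |
| Mysore | 78.8 | 52.3 | 1.51 |

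Under that condition A exceeds C with no selection at all, so A above C does not by itself show selection. The condition matters. If use per enrollee in C is at least 1.34 times that in A, A is no longer above C. In the other direction the check has force: ITT use clearly higher in C than in A contradicts the selection prediction. The plan does not say whether the midline rates are per enrollee or per assigned household.

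**3. Direction of the household-size prediction.** Section 4.2 gives a premium of about INR 200 and cover for up to five members. Price per member is 200/size; price per covered member is 200/min(size, 5).

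| Household size | 2 | 3 | 4 | 5 | 6 |
|---|---|---|---|---|---|
| INR per member | 100 | 67 | 50 | 40 | 33 |
| INR per covered member | 100 | 67 | 50 | 40 | 40 |
| Arm A (free) | 0 | 0 | 0 | 0 | 0 |

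The price falls or levels off with size, on either denominator. If a higher price causes more use, per-capita use among enrollees should fall with size. The bullet says it should rise. The bullet does not state its population. Across all households, a lower price per member could raise enrolment and so per-capita use, but that too is ordinary demand and would not support the heading.

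**The case against.** The best defence of Section 10.4 is elimination: failing to support two named candidates should raise the third. Part of this stands. When power exceeds alpha, a non-significant test does lower the odds of the explanation tested. At an assumed alpha of 0.05 the likelihood ratio is 0.5/0.95 = 0.53 at 50% power and 0.2/0.95 = 0.21 at 80%. A reader might infer that non-support carries no information at all; that goes too far. What remains is that its strength is unknown, because no power is given, and that whatever it takes from the two rivals goes equally to chance and to unlisted causes. If both must fail, the rule is also much less extreme than if either may, but the wording does not settle which is meant.

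The plan is candid that sunk costs has no test, claims only evidence in favour, and calls the exercise exploration. That limits the harm but does not make the inference sound.

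A reader might also dismiss the A-versus-C check as empty. The documents do not support that: it predicts weakly higher use in A, is distinguished from the enrollee-only comparison, and can be contradicted by the data.

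On household size, the likeliest defence is a slip of wording. It would still need correcting, since the bullet gives its reason explicitly and the reason runs the wrong way.

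Finally, a reader might infer that the whole of evaluation question 2, or the main results, are compromised. They are not. Whether price affects use is addressed by the randomised ITT comparisons in Section 7.1 and the first bullet of Section 10.1, neither of which uses these rules.

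**Conclusion.** Both defects stand on the text and need no assumed number. Section 10.4 credits a mechanism by default on evidence that is at most weak and of unknown strength, without requiring that the finding persist. The household-size bullet in Section 10.1 has the wrong sign for its heading and for the finding it is meant to check.

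No error rate can be attached to Section 10.4, because the plan gives no alpha, power or combining rule for its five checks; the percentages above are illustrations. The 1.34 ratio holds only at equal card use per enrollee. The sign error rests on the plan's own fixed price.

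The reach is limited to the mechanism part of evaluation question 2 and to one of the two persistence checks. Within that reach these are stated rules that would give a wrong reading, and they should be corrected before the endline mechanism results are interpreted.

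**What to change.** **Section 10.4**
- Delete the default attribution and state that sunk costs is not separately tested.
- Report the Section 10.2 and 10.3 estimates with confidence intervals. Separate estimates that contradict a prediction from those that are inconclusive. For example, ITT use clearly higher in C than in A counts against selection as the sole explanation.
- Apply the mechanism analysis to the endline only if the group C finding persists there.
- If a note on the A-versus-C check is added, give both sides: at equal card use per enrollee, enrolment alone yields a ratio of 1.34, so A above C does not by itself show selection, while C above A contradicts the prediction.

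**Section 10.1, household-size bullet**
- Reverse the predicted sign, or relabel the bullet as the ordinary-demand alternative that counts against the midline finding.
- State the population (all assigned households or enrollees) and the denominator (all members or covered members).
- Use the arm-by-household-size interaction already planned in Section 7.3 (equation 4), with free arm A as the reference: its price per member is zero at every size, so its size gradient reflects influences other than price. At stated village shares, the heading implies a C-by-size coefficient below the A-by-size coefficient; ordinary demand implies the reverse.
- Label the check as non-randomised supporting evidence, because household size was not randomised.

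Date both changes as made after the scheduled March-May 2019 endline fieldwork. The cost is a few sentences, with no new data and no new estimator. The investigators give up a default reading in favour of sunk costs.
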